## 2.3 Rationale

Sn-117m-DPTA localizes selectively in bone, a unique physical characteristic. In addition, a major advantage of Sn-117m-DTPA is the low energy conversion electrons emitted (0.2-0.3 mm), which minimizes the radiation dose to the bone marrow and results in deeper tissue penetration (~300 mcm). Thus, this radiopharmaceutical has low bone marrow toxicity compared to the beta and alpha emitters. Sn-117m-DTPA has a gamma photon of 158.6 keV, and its half-life is 13.6 days. Atkins *et al.* (1993) studied the whole-body distribution of Sn-117m-DTPA and showed that more than 50% of the administered activity was absorbed in the bones of patients with metastatic cancer. The red marrow absorbed dose was low compared with the bone surface dose. All other tissues received less than 1/10 of the dose received by red marrow.

A pilot study of 15 patients with painful skeletal metastases from myriad solid tumors evaluated treatment with Sn-117m-DTPA at 71-143 mCi/kg (Atkins *et al.*, 1995). Results demonstrated pain relief without inducing bone marrow toxicity. Krishnamurthy *et al.* (1997) studied the biokinetics and imaging characteristics of Sn-117m-DTPA radioactivity in 17 patients with metastatic bone pain. Three dose levels were administered IV: 180 mCi/kg, 229 mCi/kg, and 285 mCi/kg of patient body weight. Pain palliation was observed with all three doses, with responses in 60-83% of cases. The duration of pain palliation ranged from 3 to 14 months from a single administration of Sn-117m-DTPA. The majority (59%) of the administered Sn-117m-DTPA was taken up in bony metastatic lesions and peaked in three to seven days, whereas peak uptake in normal bones occurred by 24 hours. The remaining radioactivity was excreted by the urinary tract (37%).

In a phase 1/2 study, 47 patients with painful bone metastases from a variety of malignancies (including 30 patients with prostate cancer) were treated with five different levels of Sn-117m-DTPA radioactivity (Srivastava *et al.*, 1998). The dose levels, based on kg of body weight, were as follows: 2.64 MBq (71 mCi), 5.29 MBq (143 mCi), 6.61 MBq (179 mCi), 8.46 MBq (229 mCi), and 10.58 MBq (286 mCi). Approximately 45% of patients obtained reduction of pain by at least 50%, and 30% experienced complete relief of pain for more than two weeks. There was no correlation between response rate and the dose levels. However, the time to onset of pain relief was shorter ( $5 \pm 3$  days) with doses  $\geq 12.5$  mCi/70 kg than with doses  $\leq 10$  mCi/70 kg ( $19 \pm 15$  days).

In a randomized phase 2 study of three dose levels of Sn-117m-DTPA compared to Sr-89-chloride, a dose of 30 mCi Sn-117m-DTPA was well tolerated (Data on file, Serene LLC). The study was stopped early due to commercial considerations, and only safety results were analyzed. The results of this study demonstrate, however, that a dose of at least 30 mCi/70 kg (approximately  $1.73 \text{ m}^2$ ) could be administered safely.

Collectively, there is mounting evidence that Sn-117m-DTPA has promising palliative efficacy with minimal toxicity. Thus, additional evaluation of this agent in patients with bony metastases is urgently required.

## 2.4 Correlative Studies Background

### 2.4.1 Whole Exome Sequencing (WES)

**Biologic Rationale:** Gene expression profiling is an important tool to elucidate the novel biomarkers of radio-sensitivity in order to predict treatment response. Radiation induces DNA damage and thus causes cell death. Upregulation of DNA damage response pathways was associated with radiation sensitivity (Kamran and Mouw, 2018). Extent of somatic copy number alterations and increased expression of PI3K and JAK/STAT pathway components were associated with radiation resistance.

**Hypothesis:** We propose to test for DNA damage repair (DDR) gene alterations (*BRCA1/2* loss/mutation, *ATM*, *ATR*, *CHEK1/2* loss/mutation, *RAD50*, *PALB2*, *CDK12*, *FANCA*, *POLE* mutation), somatic mutations in MMR genes (*MLH1*, *MSH2*, *MSH6*, *PMS2*), replication stress

(*CCNC1*, *CCNE1*, *MYCN* amplification) and *TP53*, *PIK3CA*, *FBXW7*, and *KEAP1* mutations and will correlate with treatment outcomes. Additionally, we propose to test for germline variants such as *MLH1*, *MSH2*, *MSH6*, *PMS2* (for Lynch syndrome), and homologous recombination genes such as *BRCA1*, *BRCA2*, *ATM*, *PALB2*, and *CHEK2*. Archival tissue will be employed as available (no new baseline biopsies will be performed).

#### 2.4.2 RNA Sequencing (RNAseq)

**Biologic Rationale:** Radiation-induced gene expression changes mainly involve p53 signaling, cell cycle regulation, DNA repair, and inflammatory response (Bosma *et al.*, 2020). The ability to predict tumor response to radiation therapy is a necessary avenue to improve treatment outcomes. RNAseq allows for a much broader dynamic detection of both protein-coding and non-coding RNAs that play significant roles in prostate cancer progression.

**Hypothesis:** We will explore the differences in RNA expression between radiosensitive and radioresistant treatment outcomes in prostate cancer patients who undergo treatment with Sn-117m-DTPA.

[figure not shown]
**Relevant Preclinical Data:** Young *et al.* (2014) studied novel predictive biomarkers *in vitro* by analyzing the expression of genes involved in DNA repair pathways by RNAseq in radioresistant (PC-3) and radiosensitive (LNCaP) prostate cancer cell lines. The study demonstrated that radiosensitive LNCaP cells down-regulated *BRCA1*, *FANCG*, *RAD51*, *MCM7*, *CDC6*, and *ORC1*, whereas the radioresistant PC-3 cell line up-regulated these genes.

#### 2.4.3 Polo-like Kinase (PLK1)

[figure not shown]
**Biologic Rationale:** PLK1, a critical cell cycle regulator, is overexpressed in prostate cancer, and its level of expression is associated with tumorigenicity in prostate cancer (Zhang *et al.*, 2015) (**Figure 1**). PLK1-associated phosphorylation of Mre11 leads to premature DNA damage checkpoint termination and reduced DNA repair (Weichert *et al.*, 2004). Thus, cancer cells with higher levels of PLK1 tend to continue to enter mitosis with damaged DNA, resulting in a higher level of cell death.

**Hypothesis:** We propose to evaluate the feasibility of measuring the expression level of PLK1, a critical cell cycle regulator, to be used as a biomarker to predict the efficacy of radiotherapy. Tissues will be subjected to immunohistochemistry to measure the levels of PLK1 prior to radiotherapy. These studies will interrogate whether it is feasible to do this exploratory study, and this will help guide future biomarker studies.

**Relevant Preclinical Data:** Our preliminary data showed that mice with Plk1 overexpression are much more sensitive to radiotherapy than Plk1-negative mice (**Figure 2**) (Li *et al.*, 2017).

**Figure 1. PLK1 level is correlated with tumorigenicity in different prostate cell lines.** Immunoblot of PLK1 in RWPE-1, LNCaP, C4-2, and PC3 cells.

[figure not shown]

**Figure 2. Plk1-KI mice are hypersensitive to irradiation (IR).** (A) Mouse embryonic fibroblasts (MEFs) from control and CMV-Cre/Plk1-KI mice were plated at clonal density and subjected to increasing doses of IR. The number of colonies appearing after 10 days on the irradiated plates indicate the reduced viability of Plk1-overexpressing MEFs upon IR exposure. To quantify the number of cells remaining on the plates after IR, samples were stained with MTT and lysed, and absorbance was measured with a standard plate reader. The values reported are means  $\pm$  S.D. of three independent experiments (bottom panel). \*\*p < 0.01. (B) Mice at the age of 10 weeks were subjected to 5 Gy whole-body IR and imaged after 4 months.

#### 2.4.4 Systemic Inflammatory Markers

**Biologic Rationale and Relevant Preclinical Data:** Our preclinical animal data studied the changes of IL-8 (pro-inflammatory cytokine) and PSA levels in tumor-bearing mice after treatment with radiotherapy (Xu *et al.*, 2012). It showed that an inverse relationship between IL-8 and PSA levels is associated with the response of PCa cells to radiation (Figure 3).

**Hypothesis:** We predict that patients with low IL-8/PSA ratios have a potential to respond to radiotherapy much better than those with high IL-8/PSA ratios. We propose to examine the irradiation-induced changes in systemic inflammatory markers such as IFN-gamma, TNF-alpha, IL-8, IL-10, and IL-17 prior to treatment *vs.* after one and two cycles of treatment, and 8 weeks after completing treatment, and correlate values/changes with treatment outcomes.

**Figure 3. The effects of PSA and IL-8 on radioresistance of PCa cells.** To determine the roles of PSA and IL-8 in radiosensitivity of PCa cells, LNCaP cells were treated with IL-8 protein or stably transfected with IL-8 cDNA (A) and stably transduced with PSA shRNA lentivirus (B). PC3 cells were stably transduced with PSA cDNA and IL-8 shRNA lentivirus (C). The levels of PSA were quantified by western blots, and the levels of IL-8 were quantified by either western blots or an ELISA kit.

#### 2.4.5 Immune Cells

**Biologic Rationale:** The effects of ionizing radiation are seen not only in tumor cells but also in the tumor microenvironment. In general, lymphocytes (T cells, B cells, and natural killer [NK] cells) are among the most radiosensitive cells, followed by monocytes, macrophages, and antigen-presenting cells (APCs), specifically dendritic cells (DCs), which have a higher radioresistance (Bauer *et al.*, 2011; Manda *et al.*, 2012). Additionally, radiation therapy can cause overproduction of inflammatory chemokines and cytokines including granulocyte colony-stimulating factor (G-CSF), macrophage CSF (M-CSF), granulocyte-macrophage CSF (GM-CSF), IL-6, IL-10, vascular endothelial growth factor (VEGF), transforming growth factor (TGF)-beta, tumor necrosis factor (TNF)-alpha, chemokine ligand (CCL) 2, CCL5, and prostaglandin E2. The overproduction of these chemo-cytokines results in altering myelopoiesis and causing release of MDSCs. MDSCs suppress antitumor responses of T and NK cells and expand regulatory T cells, promoting cancer progression (Umansky *et al.*, 2016). IL-6 is critically important for MDSC generation and survival. There is a correlation between increased IL-6 concentrations and MDSC frequencies and their suppressive functions (Chi *et al.*, 2014). MDSCs are increasingly recognized as important contributors to immunosuppression in the

tumor micro-environment and are also closely associated with resistance to RT (Kang *et al.*, 2020).

**Hypothesis:** We propose to evaluate the correlation between frequencies of MDSCs, immune function markers, and treatment outcomes. The markers of immune function will be evaluated by measuring the percentage and absolute number of CD4+ T helper cells, CD8 T+ cytotoxic cells, NK cells, T regulatory cells, PMN-MDSCs, and M-MDSCs by flow cytometry prior to treatment *vs.* after one and two cycles of treatment, and 8 weeks after completing treatment, and correlate changes with treatment outcomes. PMN-MDSCs are defined as CD15+ HLA-DRlow CD14+- and M-MDSCs are defined as CD15 HLA-DRlow CD14+ CD11b+ CD33+ by flow cytometry.

#### 2.4.6 Patient-Reported Outcomes by Common Terminology Criteria for Adverse Events (PRO-CTCAE)

The Patient-Reported Outcomes version of the Common Terminology Criteria for Adverse Events (CTCAE) was designed for patients to report their symptomatic AEs in a complementary manner to clinician graded CTCAE AE items (<https://healthcaredelivery.cancer.gov/pro-ctcae>). While the measurement system has been validated, the current use of PRO-CTCAE in clinical trials remains exploratory. Clinician reported AE items remains the safety standard. There is no real-time review of the patients' responses. Patients are encouraged to report their concerning symptoms to their physicians and/or nurses.

In this study, the symptomatic AEs to be collected are nausea, vomiting, constipation, diarrhea, numbness and tingling, dizziness, general pain, joint pain, fatigue, painful urination, urinary urgency, urinary frequency, and change in usual urine color.

For any one of these items, patient may be asked 1-3 questions for the presence, frequency, severity, and level of interference. For these 5 PRO-CTCAE items, patients will be asked a total of 11 questions. These PRO-CTCAE items correspond to nausea, vomiting, constipation, diarrhea, numbness and tingling, joint pain, fatigue, painful urination, urinary urgency, urinary frequency, change in usual urine color, CTCAE items that clinicians are reporting. Patients will report every 2 weeks from the beginning of treatment until Week 28, and then every 3 months for a total of 12 months after the first Sn-117m-DTPA administration.

Studies have demonstrated that clinicians under-report symptomatic AEs compared to patient reporting of symptoms in Health-Related Quality of Life instruments. Patient reporting may provide more complete information, particularly for lower grade chronic toxicities that may impair tolerability over time. The PRO-CTCAE data will be evaluated for data quality, to characterize baseline symptom status of patients on study, to explore the development of symptomatic AEs and their change over time, and to explore the patient scores with clinician graded AEs.

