#### 9.4.7 Patient-Reported Outcomes and Adverse Events

Safety and toxicity will be assessed by PROs and AEs (PRO-CTCAE) captured by digital instruments every 2 weeks through Week 28 for acute and long-term toxicity.

The PRO-CTCAE data will be evaluated for data quality, to evaluate the symptoms' changes over time on study, to explore the development of symptomatic AEs and the change over time, and to explore the patient scores with clinician graded AEs. PRO-CTCAE data will be summarized descriptively as the number (percent) of patients reporting each grade for individual items.

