## 11. STUDY CALENDAR

Baseline evaluations are to be conducted within 4 weeks prior to start of protocol therapy. Scans and x-rays must be done  $\leq$  8 weeks prior to the start of therapy. In the event that the patient's condition is deteriorating, laboratory evaluations should be repeated within 48 hours prior to initiation of the next cycle of therapy.

Visit dates and scans can be within  $\pm$  7 days of planned dates. Study treatment must start within 30 days of registration.

	Pre-study	Cycle 1 (8 weeks or 56 days)					Cycle 2 (8 weeks or 56 days)					Post-treatment					Follow-up a	Off-study visit	
		W1	W2	W4	W6	W8	W1	W2	W4	W6	W8	18 weeks	20 weeks	22 weeks	24 weeks	26 weeks	28 weeks		
Sn-117m-DTPA		A					A											A*	
Informed consent	X																		
Demographics	X																		
Medical History	X																		
Pain medication**	X	X	X	X	X	X		X	X	X	X		X		X		X	X (every 3 months)	X
Physical Exam	X	X		X	X			X		X		X		X		X		X	X
Vital signs	X	X		X	X			X		X		X		X		X		X	X
Height	X																		
Weight	X	X		X	X			X		X		X		X		X		X	X
Performance status	X																	X	
CBC/diff, platelets	X	X	X	X	X	X i		X	X	X	X		X		X		X	X	X
Serum chemistry b	X	X	X	X	X	X i		X	X	X	X		X		X		X	X	X
PSA	X			X	X			X		X		X		X		X		X	X
Adverse Events		X-----X																	
Patient-reported pain intensity scale and analgesic use c	X		X	X	X	X		X	X	X	X	X	X	X	X	X	X	X	X
Patient-reported CTCAE d			X	X	X	X		X	X	X	X	X	X	X	X	X	X	X	X
Sn-117m-DTPA dosimetry (optional) e		X	X	X	X														
Urine collection for urinalysis f	X						X												

NCI Protocol #: 10437  
 Version Date: January 10, 2022

	Pre-study	Cycle 1 (8 weeks or 56 days)					Cycle 2 (8 weeks or 56 days)					Post-treatment					Follow-up a	Off-study visit	
		W1	W2	W4	W6	W8	W1	W2	W4	W6	W8	18 weeks	20 weeks	22 weeks	24 weeks	26 weeks	28 weeks		
Radiologic evaluation (CT of abdomen/pelvis and bone scan) and chest X-ray g or PSMA PET CT scan	X					X					X				X			X (every 3 months)	
Research blood for genomic whole exome sequencing (mandatory when archival tissue or slides are submitted)	X																		
Research blood for exploratory studies (optional) h	X					X h					X h				X				
Archival tissue for genomic sequencing and exploratory PLK1 stain (optional)	X																		

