A: Sn-117m-DTPA: 20 mCi/70 kg (0.28 mCi/kg) slow IV injection over 10 min on C1D1 and C2D1

\*Patients can be retreated if pain recurs within 6 months after 16-week pain observation period

a: Follow-up visit evaluation. Every 3 months or as clinically indicated up to one year from the first dose injection or disease progression

b: Albumin, ALP, total bilirubin, bicarbonate, BUN, calcium, chloride, creatinine, glucose, LDH, sodium, potassium, total protein, SGOT [AST], SGPT [ALT].

c: Pre-treatment daily baseline pain and analgesic use for 7 days (at least 4 out of 7 days) is required before treatment initiation. Patients will be asked to report their pain at its worst in the last 24 hours and analgesic use (stable/reduced/increased) by digital version every 2 weeks through Week 28, followed by routine clinic follow up or when they experience new pain during off-visit. **A full short version of brief pain inventory (BPI) will be asked at baseline, after Cycle 1, after Cycle 2, and at Week 24.**

d: PRO-CTCAE survey items will be assessed by digital instruments. Beginning at Week 28, surveys are requested every 3 months for 6 months after the last study treatment administration.

e: Serial DTPA dosimetry scans (optional) will be obtained at 1 hour, 4 hours (or within 4-6 hours), 24 hours (or within 16-24 hours), 48 hours (or within 36-48 hours), 72 hours (or within 60-72 hours), 1 week (+/2 days), and 4 weeks (+/2 days) post-infusion. The dosimetry scan will only be performed with first cycle of injection.

f: Urine collection for urinalysis will be collected at the indicated time points or as clinically indicated to monitor for microscopic or macroscopic hematuria as part of genitourinary toxicity monitoring.

g: Imaging: Follow up tumor response will be evaluated by CT scan of abdomen and pelvis, bone scan and chest X-ray. If Chest X-ray shows abnormal or clinically symptomatic, then CT chest should be obtained. Follow-up scans at every 8 weeks will be performed as clinically indicated, per institutional standards. PSMA PET CT scan at baseline is also acceptable.

*NCI Protocol #: 10437*

*Version Date: January 10, 2022*

h: Blood collections for research during Cycles 1 and 2 should be collected on the last day of each cycle.

i: CBC and serum chemistry should be performed 1 week before the start of Cycle 2.

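### No PRO-CTCAE survey is scheduled before the first dose, so baseline symptom status and change from a pre-treatment value cannot be estimated by PRO-CTCAE

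*Combined protocol and SAP*

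**What the plan says.** Section 2.4.6 gives the purposes of the PRO-CTCAE data, which include "to characterize baseline symptom status of patients on study" and exploring how symptomatic events develop and change. On timing it says: "Patients will report every 2 weeks from the beginning of treatment until Week 28".

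In the Section 11 calendar, the row "Patient-reported CTCAE" has no mark at Pre-study or at Cycle 1 Week 1, where the first injection is given. Its first mark is Cycle 1 Week 2. The row directly above it, "Patient-reported pain intensity scale and analgesic use", does have a Pre-study mark, and note c backs that mark with a requirement: "Pre-treatment daily baseline pain and analgesic use for 7 days (at least 4 out of 7 days) is required before treatment initiation". Note d, which governs the PRO-CTCAE row, covers only the mode of collection and the late schedule: "PRO-CTCAE survey items will be assessed by digital instruments. Beginning at Week 28, surveys are requested every 3 months".

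The statistical text names no pre-treatment survey either. Section 9.4 speaks of collection during treatment and afterwards. Sections 9.4.7 and 9.6.1 give a two-weekly schedule to Week 28. Section 9.4.7 drops the baseline aim and keeps "changes over time on study, to explore the development of symptomatic AEs and the change over time". Its planned analysis is counts and percentages of patients at each grade, item by item. Objective 1.2.8 is simply to measure PROs and PRO-CTCAE events.

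**The concern.** The plan states a baseline aim and then schedules the first measurement after the drug has been given. In a single-arm trial a patient's own pre-dose report is the only within-trial reference for a symptom score. Without it, a Week 4 report of moderate urinary urgency cannot be classed as new, worse or unchanged, and the percentages by grade mix symptoms the patient brought to the trial with those that emerged after dosing.

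Pre-existing symptoms are plausible on several items. Criterion 3.1.4 requires a worst-pain score of at least 4. Criterion 3.2.6 allows residual Grade 1 toxicity from earlier therapy, and 3.2.11 allows neuropathy below Grade 2. Section 2.1.2 notes that narcotic analgesics bring side effects of their own. Four of the 13 items are urinary, and Section 10.3.4 lists urinary frequency, urgency and dysuria among signs of acute radiation toxicity, so attribution matters there. The pre-dose value cannot be recovered for a patient once the first injection has been given.

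**Working it through.** The plan states no figure to reproduce here. The check is a reading of the calendar plus two counts.

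**1. Is the blank real or a table-extraction shift?** The calendar has 1 Pre-study + 5 Cycle 1 + 5 Cycle 2 + 6 post-treatment + 2 (follow-up, off-study) = 19 columns. The PRO-CTCAE row and the pain row each resolve to 19 cells.

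| Row | Pre-study | C1 W1 | C1 W2, 4, 6, 8 | C2 W1 | C2 W2, 4, 6, 8 | Weeks 18–28 | Follow-up, off-study |
|---|---|---|---|---|---|---|---|
| Pain and analgesic use | X | – | 4 X | – | 4 X | 6 X | 2 X |
| PRO-CTCAE | – | – | 4 X | – | 4 X | 6 X | 2 X |

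The rows match in every column except Pre-study, so the gap is in the schedule itself.

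**2. Surveys through Week 28.** Pre-treatment: 0. After dose 1: 4 + 4 + 6 = 14. With one pre-dose survey added the total is 1 + 14 = 15, matching the pain row, and change from a pre-treatment value can then be estimated at all 14 later points.

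**3. Could the Week 2 survey fall before the dose?** The calendar allows ±7 days. If Week 2 means about Day 14–15 (an assumption), the earliest date is Day 7–8, after dosing. If it means Day 8 (also an assumption), the earliest is Day 1, and nothing requires the survey to precede the injection.

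**4. Could Week 2 serve as a baseline?** Section 2.2.3.2 puts peak uptake in metastatic lesions at 3–7 days. Section 2.2.5 reports that mean time to onset of pain relief plateaued at 5 days for doses of 12.5 mCi/70 kg and above, and the regimen in Section 6.1 is 20 mCi/70 kg. At least for pain, a Week 2 value would already contain treatment effect.

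**5. Size of the survey.** From the attributes in Section 10.4.4: constipation 1, diarrhea 1, general pain 3, fatigue 2, numbness and tingling 2, and eight further items at 2 each. That is 1 + 1 + 3 + 2 + 2 + (8 × 2) = 25 questions over 13 items. Section 2.4.6 also speaks of 5 items and 11 questions, which does not fit its own list of 13; the count here follows 10.4.4 and Appendix G.

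**The case against.** A reader might infer that change over time cannot be studied at all. The documents do not support that. Fourteen surveys from Week 2 to Week 28 give 13 successive intervals of within-patient change, and the summaries by grade in 9.4.7 need no baseline. Only change from a pre-treatment value is lost.

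A reader might also conclude that no patient could have a pre-dose value. That is too firm. Reporting from the start of treatment, as 2.4.6 puts it, could mean a Day 1 survey. It does not say that the survey comes before the injection, and the calendar leaves that visit blank. This is a conflict between text and calendar rather than a certain zero for every patient.

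Nor is objective 1.2.8 left undefined. Neither it nor 9.4.7 specifies change from baseline; the baseline aim stands only in the background section.

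Other baseline information exists. Section 10.3.1 puts pre-treatment adverse events on a clinician-completed baseline form, and the BPI-SF and the pain run-in precede treatment. These soften the consequence but do not replace the missing survey: 2.4.6 itself says clinicians under-report symptomatic events, and the BPI-SF does not ask about nausea, bowel, neuropathy, dizziness or urinary symptoms.

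Finally, a baseline survey would not by itself separate drug effect from disease. It would identify symptoms present before dosing, but later worsening could still be progression. And PRO-CTCAE is described as exploratory (2.4.6, 13.2.3) and drives no protocol action (7.1, 10.4.1). Both points stand and limit the weight of the finding.

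**Conclusion.** The point holds in a limited form. On the calendar and note d, no PRO-CTCAE survey precedes the first injection, so the baseline aim in 2.4.6 is unsupported. Change from a pre-treatment value cannot be estimated on any of the 13 items, and PRO-CTCAE cannot distinguish symptoms present at entry from those emerging after dosing.

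Change among post-dose surveys and the descriptive summaries by grade survive. The primary endpoint is unaffected because pain has its own required baseline. The consequence falls on a secondary, descriptive endpoint.

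The conclusion assumes that sites follow the calendar. If they act on a Day 1 reading of 2.4.6 instead, some pre-dose values might be collected, but neither consistently nor by requirement.

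**What to change.** Add one PRO-CTCAE survey after registration and before the first injection. Mark it in the calendar and state it in note d, including that it must be completed before the injection. Reword 2.4.6 so that its start point agrees with the calendar, and add the baseline to 9.4.7. There, report for each item the share of patients whose score worsened from their own pre-dose value, beside the raw grades.

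Placing the survey after registration matters. Pain scores from the pre-screening period determine inclusion (5.10.2.3.2), eligibility is verified before OPEN is accessed (4.3.1), and Patient Cloud registration follows OPEN registration (4.3.4, Appendix H). App access during the pain run-in is therefore not assured. Treatment may start up to 30 days after registration (4.4), which leaves room for the survey, and paper is already allowed (4.3.4, 13.2.3).

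The cost is one further 25-question survey per patient, on top of the 14 already scheduled through Week 28, plus a short amendment to the text and calendar. No new instrument is needed.
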